3.2 Study Overview

This is a prospective, multi-center, unblinded single arm safety and feasibility study. Subjects will undergo percutaneous PEF ablation for pulmonary vein isolation and at the clinical discretion of the investigator receive PEF ablation of additional arrhythmogenic locations. Subjects will be followed at 30 days, 75 days, 6 months and 12 months for adverse events, recurrence of arrhythmia after a 90-day Blanking Period and other relevant outcome measures.

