Ablation with the FARAWAVE Ablation Catheter may be repeated at the same site or at another target site at the physician's discretion using deployment configurations to suit target anatomy. Each addressable pulmonary vein will be ablated in turn beginning with placement of the guidewire, deployment of the ablation catheter, confirmation of pacing capture, and ablation. The effect of the ablation(s) may be checked post-procedure by pacing maneuvers, ECG recordings, 3D electroanatomic mapping, or by using the mapping electrodes on the ablation catheter splines.

Ablation using the FARAFLEX Ablation Catheter may be performed to close gaps in electrical isolation of pulmonary veins, focally ablate cardiac arrhythmias, or create a line of ablation at the cavo-tricuspid isthmus (CTI).

For a detailed description of procedure workflow refer to LBL0193 (FARADRIVE Deflectable Sheath), LBL0195 (FARAWAVE Endocardial AblationCatheter), LBL0565 (FARAFLEX Endocardial Ablation Catheter and LBL0198 (FARASTAR Endocardial Generator System).

3.11.2 75-Day Remap Procedure

The 75-Day Remap Procedure will follow the steps contained in **Section 3.11.1, Index Procedure**, as determined by investigator discretion to achieve protocol-required mapping and any required reablation.

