2.4.6.1. Primary Feasibility Analysis

The primary feasibility analysis is the proportion of subjects that achieve Acute Procedural Success (APS) defined as the percutaneous endocardial creation of a complete, electrically isolating set of lesions around the ostia of the pulmonary veins (PVI) using the FARAPULSE Endocardial Multi Ablation System during the Index Procedure, as clinically assessed by entrance and/or exit block performed \geq 20 minutes after the last PVI lesion is made.

CONFIDENTIEL / CONFIDENTIAL

Toute reproduction ou distribution, totale ou partielle, de ce document, sans autorisation préalable de ICON PLC est interdite.
Reproduction and distribution of this document, in whole or in part, is strictly forbidden without prior authorization from ICON PLC.

	STATISTICAL ANALYSIS PLAN	FARAPULSE PersAFOne SAP V1.0 PERSAFONE Page 17 /49
---	----------------------------------	--

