IF AF/AFL/AT status =0 **AND** DCCV90D=0 **AND** RF touch up=0 **AND** ABL>90 day=0 **AND** Class I/III AAD >90 days =1 in **MDT excel file** **THEN** Freedom from AF/AFL/AT, no DCCV>90 days, no RF, no ablation >90 days with Class I/III AAD >90 days='Yes'
ELSE Freedom from AF/AFL/AT, no DCCV>90 days, no RF, no ablation >90 days with Class I/III AAD >90 days='No'
- Derived criteria "Freedom from AF/AFL/AT, no DCCV>90 days, no RF, no ablation >90 days without Class I/III AAD >90 days" will be defined as follows:
IF AF/AFL/AT status =0 **AND** DCCV90D=0 **AND** RF touch up=0 **AND** ABL>90 day=0 **AND** Class I/III AAD >90 days =0 in **MDT excel file** **THEN** Freedom from AF/AFL/AT, no DCCV>90 days, no RF, no ablation >90 days without Class I/III AAD >90 days= 'Yes'
ELSE Freedom from AF/AFL/AT, no DCCV>90 days, no RF, no ablation >90 days without Class I/III AAD >90 days='No'
- Derived criteria "Freedom from AF, no DCCV>90 days, no RF, no ablation >90 days" will be defined as follows:
IF AF status =0 **AND** DCCV90D=0 **AND** RF touch up=0 **AND** ABL>90 day=0 in **MDT excel file** **THEN** Freedom from AF, no DCCV>90 days, no RF, no ablation >90 days ='Yes'
ELSE Freedom from AF, no DCCV>90 days, no RF, no ablation >90 days ='No'
- Derived criteria "Freedom from AF, no DCCV>90 days, no RF, no ablation >90 days with Class I/III AAD >90 days" will be defined as follows:
IF AF status =0 **AND** DCCV90D=0 **AND** RF touch up=0 **AND** ABL>90 day=0 **AND** Class I/III AAD >90 days =1 in **MDT excel file** **THEN** Freedom from AF, no DCCV>90 days, no RF, no ablation >90 days with Class I/III AAD >90 days ='Yes'
ELSE Freedom from AF, no DCCV>90 days, no RF, no ablation >90 days with Class I/III AAD >90 days ='No'
- Derived criteria "Freedom from AF, no DCCV>90 days, no RF, no ablation >90 days without Class I/III AAD >90 days" will be defined as follows:
IF AF status =0 **AND** DCCV90D=0 **AND** RF touch up=0 **AND** ABL>90 day=0 **AND** Class I/III AAD >90 days =0 in **MDT excel file** **THEN** Freedom from AF/AFL/AT, no DCCV>90 days, no RF, no ablation >90 days without Class I/III AAD >90 days='Yes'
ELSE Freedom from AF/AFL/AT, no DCCV>90 days, no RF, no ablation >90 days without Class I/III AAD >90 days= 'No'

Primary feasibility endpoint

IF Ablation with study device was successful = 'Yes' in **procedural form (PR)** **THEN** APS='Yes'

CONFIDENTIEL / CONFIDENTIAL

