Toute reproduction ou distribution, totale ou partielle, de ce document, sans autorisation préalable de ICON PLC est interdite.
Reproduction and distribution of this document, in whole or in part, is strictly forbidden without prior authorization from ICON PLC.

	STATISTICAL ANALYSIS PLAN	FARAPULSE PersAFOne SAP V1.0 PERSAFONE Page 24 /49
---	----------------------------------	--

ELSE IF Ablation with study device was successful = 'No' in **procedural form (PR)** **THEN**
APS='No'

Secondary Feasibility Analysis

- Derived criteria "Chronic Procedural Success (CPS)" will be defined as follows:
IF Has all ablation with the study device(s) been successful? ='Yes' in **Procedural data form (PR)** **AND** Has all ablation with the study device remain successful? ='Yes' **AND** Additional ablation(s) performed? ='No' in **FOLLOW UP 3D ELECTRO ANATOMICAL MAPPING form (RM)** **THEN** Chronic Procedural Success (CPS) ='Yes, index procedure only'
ELSE IF Has all ablation with the study device(s) been successful? ='Yes' in **Procedural data form (PR)** **AND** Has all ablation with the study device remain successful? ='No' **AND** Any PV reconnections noted? in = 'Yes' **AND** Additional ablation(s) performed? ='Yes' in **FOLLOW UP 3D ELECTRO ANATOMICAL MAPPING form (RM)** **THEN** Chronic Procedural Success (CPS) ='Yes, reblated'
ELSE IF Has all ablation with the study device(s) been successful? ='No' in **Procedural data form (PR)** **THEN** Chronic Procedural Success (CPS) ='No'
- Derived criteria Proportion "Acute Cavotricuspid isthmus (CTI) Success" will be defined as follows:
COUNT IF [CTI isolated/Blocked='Yes' AND CTI Attempted='Yes'] in **Procedural data form (PR)**
- Derived criteria "Durability of CTI at remap," will be defined as follows:
IF CTI lesion durable ='Yes' in **Follow-up 3D electroanatomical mapping form (RM)** **THEN** Durability of CTI at remap = 'Yes'
ELSE IF CTI lesion durable ='No' in **Follow-up 3D electroanatomical mapping form (RM)** **THEN** Durability of CTI at remap = 'No'
- Derived criteria "Durability of Mitral isthmus at remap" will be defined as follows:
IF Mitral isthmus lesion durable ='Yes' in **Follow-up 3D electroanatomical mapping form (RM)** **THEN** Durability of Mitral isthmus at remap = 'Yes'
ELSE IF Mitral isthmus lesion durable ='No' in **Follow-up 3D electroanatomical mapping form (RM)** **THEN** Durability of Mitral isthmus at remap = 'No'

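### Acute Procedural Success is programmed from one general success item, while its definition requires complete pulmonary vein isolation shown by a timed block test

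*SAP*

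**What the plan says.** **Definition.** Protocol 6.3 and SAP 2.4.6.1 agree. APS is a complete isolating lesion set at the PV ostia, made with the study system at the Index Procedure, "as clinically assessed by entrance and/or exit block performed" at least "20 minutes after the last PVI lesion is made".

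**Derivation.** SAP 2.5 reads one item on form PR, "Ablation with study device was successful". APS is 'Yes' if the item is 'Yes' and 'No' if it is 'No'. There is no other branch and no other variable.

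**Neighbouring rule.** Chronic Procedural Success (CPS), the next derivation in SAP 2.5, starts from a form PR item worded "Has all ablation with the study device(s) been successful".

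**Extra-PV ablation.** Protocol 3.2 lets subjects, at the investigator's discretion, "receive PEF ablation of additional arrhythmogenic locations".

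**Checking the lesion.** Protocol 3.11.1 says "The effect of the ablation(s) may be checked post-procedure by pacing maneuvers" or by other listed methods, and states no waiting time. The index data list in Protocol 3.12.2 includes procedural times, lesion set data and post-ablation maps, but no block-test time.

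**The concern.** The definition is anatomical (PVs only) and timed. The programmed rule is neither. If the item covers every study-device lesion, an incomplete CTI line would turn a PVI success into an APS failure. Separately, a 'Yes' could be entered without a documented test at 20 minutes, and the derivation would not notice.

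APS is the primary feasibility result of a descriptive study whose stated use is to inform and design later ones. As programmed, it could also contradict the vein-level isolation rows in SAP Tables 4 and 11, which come from the same form. No reconciliation between them is planned.

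**Working it through.** The documents give no expected APS, target or power, so there is no stated figure to reproduce. The check compares the definition with the rule and then sizes a misclassification.

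**1. Definition against rule**

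| Element | Definition (Protocol 6.3, SAP 2.4.6.1) | Rule (SAP 2.5) |
|---|---|---|
| Anatomy | PV ostia, complete set | Not limited to PVs |
| Evidence | Entrance or exit block | None named |
| Timing | At least 20 minutes after last PVI lesion | None |
| Blank item | Not addressed | Neither branch applies, so APS is missing |

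SAP 2.1.3 takes percentages over non-missing observations, so a subject with a blank item also leaves the denominator.

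**2. Scope of the item.** The APS item has no PV restriction. The word 'all' appears only in the CPS item. The two are probably one field, since they sit on the same form and are worded alike, but the SAP does not say so.

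**3. Data available.** According to SAP 2.5, form PR holds an Isolated/Blocked result for each vein and separate CTI fields. The ablation records (form AB) give the location of each application and the last PVI ablation time. PV and extra-PV outcomes can therefore be separated with existing data. The block-test time is the piece not listed.

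**4. Size per subject.** One misclassified subject shifts APS by 1/N: 1/40 = 2.5 points, or 1/25 = 4 points. Forty is the planned maximum; 25 is the N printed in SAP Tables 5 and 19.

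**5. Illustration.** Assume every PV is isolated in every subject, and that k subjects are marked 'No' only because of an extra-PV failure. APS = (N − k)/N. SAP 2.1.4 prescribes Agresti-Coull at 100% when the asymptotic assumptions fail, and the exact interval in other such cases. The SAP does not spell out those assumptions; I take them as failing for all rows below.

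For Agresti-Coull, with z = 1.96: ñ = N + z², p̃ = (x + z²/2)/ñ, limits p̃ ± z√(p̃(1 − p̃)/ñ). At 40/40, ñ = 43.84 and p̃ = 41.92/43.84 = 0.956, so the lower limit is 89.6% and the upper is cut at 100%.

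| N | k | APS | 95% interval |
|---|---|---|---|
| 40 | 0 | 100% | 89.6–100% |
| 40 | 1 | 97.5% | 86.8–99.9% |
| 40 | 2 | 95.0% | 83.1–99.4% |
| 40 | 4 | 90.0% | 76.3–97.2% |
| 25 | 0 | 100% | 84.2–100% |
| 25 | 1 | 96.0% | 79.6–99.9% |
| 25 | 2 | 92.0% | 74.0–99.0% |

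**6. How many might be affected.** The documents give no extra-PV failure rate. Assume 30–80% of subjects have an extra-PV target, 2–10% of those targets fail, and the item covers them. At N = 40 the expected number is between 40 × 0.30 × 0.02 = 0.24 and 40 × 0.80 × 0.10 = 3.2. The chance of at least one is between 1 − (1 − 0.006)^40 = 21% and 1 − (1 − 0.08)^40 = 96%. The range is wide because the inputs are unknown.

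**7. The timed test.** An untimed 'Yes' errs the other way, because a vein that reconnects before 20 minutes could still be counted as a success. The documents give nothing from which to size this. With two possible errors of opposite sign, the net bias cannot be signed.

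**The case against.** A reader might infer three stronger things, and the documents do not support them.

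- **That non-PV failures do enter APS.** The form and its completion instructions are not available. The item might sit in a PVI block or carry the APS definition. This stands: leakage is a likely risk, not a shown fact.
- **That the timed test is never checked.** Protocol 5.2 and 9.10 plan committee review of primary and major outcomes, Protocol 8 lists the primary feasibility endpoint for source verification, and SAP 2.1.2 lets committee-reviewed data prevail. An investigator may also apply the timed definition when completing the item. This stands against any claim about the whole study. It does not rescue the derivation, which reads only form PR, and the documents list no test time for reviewers to verify.
- **That Protocol 3.11.1 permits no check at all.** The permissive wording introduces a list of methods and can be read as a choice among them, and post-ablation maps are to be collected under 3.12.2. What is missing is a link to the timed test and a recorded time.

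It is also fair that vein-level isolation and acute CTI success are tabulated separately and procedure listings are planned, so a careful reader could notice a conflict. That makes a discrepancy visible but does not settle which figure is the primary result.

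**Conclusion.** The mismatch between definition and derivation is plain on the face of the documents: SAP 2.5 uses no vein-level result, block test or time for an endpoint defined by all three. That extra-PV failures would count against APS is probable. It rests on the APS and CPS items being the same field, or on the APS item being read as broadly as it is worded.

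The firm size is 2.5 points per misclassified subject at N = 40 and 4 points at N = 25. The number of such subjects is unknown, and the counts and rates in the working are assumptions. There is no hypothesis test, so alpha and power are untouched. The effect is on the primary feasibility proportion and its interval, which is reason enough to correct the rule.

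**What to change.** 1. In SAP 2.5, set APS to 'Yes' only if every PV ablated at index has Isolated/Blocked = 'Yes' on form PR with study devices. Identify the ablated veins from the application locations, not from the presence of an Isolated/Blocked answer.
2. Count an ablated vein with a blank result as not shown isolated. State this as an exception to the opening rule of SAP 2.5, which would otherwise make APS missing.
3. Keep CTI and other extra-PV results in their own endpoints, and list every subject whose vein-based APS disagrees with the general item.
4. The existing vein fields repair the anatomy, not the timing. Where source records hold the block-test time, report APS with the 20-minute criterion applied. Report the number of subjects without a documented timed test instead of setting them to missing.
5. Reconcile Protocol 3.11.1 and 3.12.2 with the timed test in Protocol 6.3. How the procedure text should read is for the sponsor and investigators.

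Cost: a small program change using fields already collected, plus retrieval of test times from source where they exist. Subjects without a recorded time cannot be repaired afterwards, which is why item 4 reports their number.

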PLANNED PROCEDURE:	
Index Procedure:
 
Subjects will undergo an attempt to isolate all pulmonary veins or their anatomic equivalent.Subjects with a past history of atrial flutter, who are at risk of atrial flutter, who present with atrial flutter during the Index Procedure or who have inducible cavotricuspid isthmus-mediated (typical) flutter may undergo ablation of the cavo-tricuspid isthmus at the discretion of the investigator.Additional left atrial lesions may be made at the discretion of the investigator including focal sites, electrical gaps and lines of isolation. 
75-Day Remap Procedure:
 
Subjects will undergo a remapping procedure at 75 ± 15 days to assess the durability of the ablation lesions performed during the Index Procedure.During this procedure, additional ablations may be made at the discretion of the investigator to optimize patient outcomes.

PRIMARY SAFETY ENDPOINT:	
The primary safety endpoint for this study is the Composite Safety Endpoint (CSE) defined as the incidence of the following early-onset and late-onset serious adverse events (SAEs) which are device- or procedure-related, as adjudicated by the CEDMC. (See Table 4. Composite Safety Endpoint Definitions in Section 6.1).
 
Early onset (within 30 days of an Index or Remap Procedure)
 
• Death• Myocardial infarction (MI)• Persistent diaphragmatic paralysis• Stroke or transient ischemic attack (TIA)• Peripheral or organ thromboembolism• Pericarditis• Cardiac tamponade / perforation• Vascular access complications requiring intervention• Heart block 
Late onset (any time during follow-up through 12 months)
 
• Pulmonary vein (PV) stenosis (> 70% diameter reduction from baseline)• Atrio-esophageal fistula
SECONDARY SAFETY ENDPOINTS:	
1. The Primary Safety Endpoint assessed at 7 days2. The proportion of subjects with a device- or procedure-related SAE3. The proportion of subjects with stroke or TIA4. The proportion of subjects requiring cardioversion5. The proportion of subjects requiring an arrhythmia-related (AF, AFL or AT) hospitalization

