3.11 Procedures

3.11.1 Index Procedure

The investigator will confirm that the following have been achieved:

- For women of childbearing potential – a negative pregnancy test
- Baseline NIHSS score
- The patient is not on amiodarone

FARAPULSE Endocardial Ablation procedure patients will undergo anesthesia according to institutional protocol. They will then be prepared in conventional sterile fashion for a cardiac catheterization procedure. Femoral vein access will be obtained via Seldinger technique. Transseptal access to the left atrium will then be obtained using either a FARADRIVE Deflectable sheath or a commercially approved sheath and Brockenbrough needle. The transseptal sheath will then be withdrawn, leaving guidewire access to the left atrium. The FARADRIVE Deflectable Sheath, or a commercial equivalent as described above in **Table 2**, will then be prepared and advanced via guidewire to the left atrium. Commercially approved multielectrode pacing catheters will then be placed via conventional technique at the investigator's discretion. A baseline electrophysiological assessment of pulmonary vein connection to the left atrium will be made and documented via FARAWAVE or a commercially approved diagnostic catheter placed in each addressable pulmonary vein. A baseline 3D electroanatomical map may also be made at the investigator's discretion. The diagnostic catheter will then be removed from the FARADRIVE Deflectable Sheath or commercial equivalent.

The FARAWAVE Ablation Catheter will then be prepared and advanced over the guidewire to the left atrium through the sheath. The guidewire will be advanced into a target pulmonary vein, the catheter splines will be deployed to suit target anatomy by retracting the deployment knob, and the deployed catheter will be advanced to the ostium of the target pulmonary vein. At the investigator's discretion, contrast venography may be performed to verify placement of the catheter at the ostium. Cardiac pacing capture from the external cardiac stimulator will be obtained via connection to a diagnostic catheter. Once pacing capture is confirmed, ablation will be performed. Ablation dose will be selected at the investigator's discretion in accordance with LBL0198, FARASTAR Generator User Manual.

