3.11.3 Blanking Period

The Blanking Period consists of Day 0 (the date of Index Procedure) through and including Day 90.

During the Blanking Period, any recurrence of AF will be documented; however, recurrences of AF, AFL or AT during this time will not be considered Therapeutic Failures.

Subjects may undergo one repeat ablation during the Blanking Period without creating a Therapeutic Failure, following the procedure detailed in the preceding sections. This may occur during the Remap Procedure or at another procedure as clinically indicated.

If a second repeat ablation procedure is performed during this time, or any nonstudy device is used for cardiac ablation, the subjects will be considered a Therapeutic Failure but will remain in the study.

Towards the end of the Blanking Period, any AFD treatment will be discontinued unless the Investigator deems the withdrawal of AFD treatment not to be in the best interests of the patient.

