3.12.3 Pre-Discharge

Prior to hospital discharge the following data will be collected:

- Adverse Events
- Data regarding the use, changes in or discontinuation of anticoagulation, rate control and/or antiarrhythmic medications.
- Cardiac rhythm as determined by a 12-lead ECG
- Occurrence, date, indication and outcome of any cardioversion(s)
- At the investigator's discretion: a post-procedural mediastinal gadolinium-enhanced MRI
- Stroke/TIA assessments

- NIHSS score
- A neurologic examination will be performed and recorded if:
 - If the NIHSS score has increased by 2 or more points
 - If there is a clinical suspicion of stroke or TIA

3.12.4 30-Day Visit

Discharged subjects will return for an office visit 30 days (\pm 7 days) post-ablation treatment. (Any subject who continues to be hospitalized 30 days post-ablation will have their 30-Day Visit assessment performed in-hospital). The following data will be collected at the 30-Day Visit:

- Adverse Events
- Symptoms of recurrent arrhythmia
- Data regarding the use, changes in or discontinuation of anticoagulation, rate control and/or antiarrhythmic medications.
- Cardiac rhythm as determined by a 12-lead ECG at the time of the visit
- Cardioversions, ablations or hospital admissions since last visit
- Heart failure status as assessed by NYHA classification at the time of visit

3.12.5 75-Day Visit and Remapping Procedure

Patients undergoing protocol-specified remapping:

Subjects will undergo the protocol-stipulated remapping procedure at 75 ± 15 days post-Index Procedure as defined in **Section 3.11.2, 75-Day Remap Procedure**.

- A 3D electroanatomical remapping procedure will be performed to assess electrical isolation of the pulmonary veins. Any electrical gaps may be closed at the investigator's discretion using study devices, or if necessary, a commercially approved ablation device (which constitutes a Therapeutic Failure).
- For patients who received extra-PV ablation at index, including those receiving ablation of the CTI, the persistence of nonconductivity in targeted tissue will be evaluated with either pacing maneuvers or electroanatomical mapping.

Procedure-specific data will be collected as follows:

- Procedural times
- Lesion set data
- Device deficiencies and malfunctions

All subjects whether undergoing remapping or not:

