- Event Monitor: An Event Monitor and training will be provided to the subject, to be used for weekly scheduled and ad hoc symptomatic monitoring through the remainder of study follow-up. (**See Section 3.11.4, Arrhythmia Core Lab**). If necessary patients will be provided with an Event Monitor by mail, telephonic training and successful transmission of a monitoring record.
- AFD Management: For patients who do not require reablation during the 75-Day remap visit AFD may be stopped at the investigator's discretion.

The following data will be collected from all subjects at 75 ± 15 days:

- Adverse Events
- Symptoms of recurrent arrhythmia
- Fluoroscopic examination of diaphragm motion is required if:
 - Patient underwent remapping to assess phrenic nerve response
 - The patient declined a remap procedure but the post Index Procedure fluoroscopic examination indicated diminished phrenic nerve response
- Data regarding the use, changes in or discontinuation of anticoagulation, rate control and/or antiarrhythmic medications.
- Pregnancy test (all women of child-bearing potential) prior to remap
- Cardiac rhythm as determined by a 12-lead ECG
- Cardiac CT or MRI scan to assess the patency of the pulmonary veins
- Cardioversions, ablations or hospital admissions since last visit
- Heart failure status as assessed by NYHA classification at the time of visit

3.12.6 6-Month Visit

Subjects will return for an office visit 6 months (180 days \pm 30 days) following the Index Procedure. The following data will be collected at the 6-Month Visit:

- Adverse Events
- Symptoms of recurrent arrhythmia
- If either the post-Index Procedure or post-75-Day Remap Procedure fluoroscopies indicated diminished phrenic nerve response, and resolution has not been previously demonstrated, a repeat fluoroscopic examination. Females of childbearing potential undergoing this examination will also receive a pregnancy test prior.
- Data regarding the use, changes in or discontinuation of anticoagulation, rate control and/or antiarrhythmic medications
- Cardiac rhythm as determined by a 12-lead ECG at the time of the visit
- Arrhythmia assessment (See **Section 3.11.4, Arrhythmia Core Lab**).
 - A 24-hour continuous ECG monitor and training will be provided to the subject
 - Event Monitor compliance will be reviewed for weekly scheduled and ad hoc symptomatic monitoring and retraining of the subject provided as needed
- Cardioversions, ablations or hospital admissions since last visit

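### A permitted repeat ablation between index and the 75-day remap has no place in the SAP's durability rules, so re-treated veins and lesions can be credited to the index procedure

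*SAP*

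**What the plan says.** **Protocol.** The Executive Summary (Planned Procedure) gives the purpose of the remap: "to assess the durability of the ablation lesions performed during the Index Procedure". Section 3.12.5 sets its timing: "Subjects will undergo the protocol-stipulated remapping procedure at 75 ± 15 days post-Index Procedure". Section 3.11.3 defines the Blanking Period, "The Blanking Period consists of Day 0 (the date of Index Procedure) through and including Day 90", and adds that "Subjects may undergo one repeat ablation during the Blanking Period without creating a Therapeutic Failure". On timing it continues: "This may occur during the Remap Procedure or at another procedure as clinically indicated". Such a repeat is to follow the procedure set out in the sections before it, and 3.11.1 includes this step: "A baseline electrophysiological assessment of pulmonary vein connection to the left atrium will be made and documented". The 30-day and 75-day visits (3.12.4, 3.12.5) both collect "Cardioversions, ablations or hospital admissions since last visit".

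Section 6.4 defines Chronic Procedural Success (CPS) as persistent isolation of all initially ablated veins and splits it into index-only and reablated subjects. It defines CTI and extra-PV durability as unaltered integrity of each lesion. Section 6.5 asks what share of veins isolated at index are still isolated at remap.

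**SAP 2.5.** A subject is coded "Chronic Procedural Success (CPS) ='Yes, index procedure only" when three answers agree: all study-device ablation succeeded (index form), it is still successful (remap form), and no additional ablation was done (remap form). The reablated category needs index success plus three remap-form answers: no longer successful, a vein reconnection noted, and additional ablation done. The vein-level proportion is veins isolated at index, minus veins with gaps at remap, divided by veins isolated at index. The CTI, mitral isthmus, roof-line, posterior-line and posterior-wall items each read one remap-form durability answer.

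The sponsor-supplied MDT file (SAP 2.3, Databases) lists ablation at remap, RF touch-up and ablation after 90 days. It has no explicit item for a study-device ablation between index and remap.

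**The concern.** The remap exists to show how well index lesions last, and the protocol asks for index-only results to be kept apart from reablated ones. A reconnection found and treated at the remap is coded as reablated. The same reconnection treated some weeks earlier can be coded as an index-only success, because no rule looks at the interval.

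On the natural reading of the form, the error runs one way. A repeat that re-isolates a reconnected vein turns a failed index lesion into an apparent durable one, and nothing in the rule produces an offsetting error. At stake are the index-only figure and the vein and lesion durability rows. These are descriptive results in a study without formal testing, but it is meant to inform the design of later studies.

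**Working it through.** The plan gives no figure to reproduce: there is no formal test and no stated number of interval repeats. The check is therefore of the rule's logic, then of its size per affected subject.

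**1. Can a repeat come before the remap?** The remap window is 75 − 15 = Day 60 to 75 + 15 = Day 90. The Blanking Period is Day 0 to Day 90, and the repeat may be a separate procedure. So yes.

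**2. The CPS rule as logic.** It uses four yes/no items: index success, still successful at remap, reconnection noted, additional ablation. That makes 16 combinations. The eight with index success = No all give CPS = No. Of the eight with index success = Yes, two give index-only, one gives reablated and five match no branch.

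**3. A test subject.** Four veins are isolated at index. One reconnects, is re-isolated before the remap, and all four are isolated at remap with no ablation there.

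| How the remap form is answered | Still successful | Reconnection | Additional ablation | SAP result |
|---|---|---|---|---|
| Status at remap | Yes | No | No | Index-only |
| History, first item only | No | No | No | No category |
| History, last item only | Yes | No | Yes | No category |
| History, all three items | No | Yes | Yes | Reablated |

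**4. Vein-level rule, same subject, status reading.** SAP: (4 − 0)/4 = 100%. Veins held by the index lesion alone: (4 − 1)/4 = 75%.

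**5. CTI and extra-PV items.** Each reads one remap-form answer. On the status reading, a re-treated lesion that is intact at remap counts as durable.

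**6. Size per subject.** Let n be the number remapped and k the number of affected subjects; both are assumptions. The planned maximum is 40, and the SAP Table 5 shell shows N = 25.

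- Index-only CPS falls by k/n when they are reclassified: 1/40 = 2.5 points, 1/25 = 4.0 points.
- Vein row, assuming four veins per subject and one re-treated vein each: 1/(4 × 40) = 1/160 = 0.6 points; 1/(4 × 25) = 1/100 = 1.0 point.

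**7. Illustration at n = 40.** Starting values come from the two earlier studies in protocol 1.3, taken as patients with all veins isolated at remap: 39/49 = 79.6% (about 32/40) and 14/35 = 40.0% (16/40). The intervals are exact 95% limits.

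| k | From 32/40 = 80.0% | From 16/40 = 40.0% |
|---|---|---|
| 0 | 80.0% (64.4 to 90.9) | 40.0% (24.9 to 56.7) |
| 1 | 77.5% (61.5 to 89.2) | 37.5% (22.7 to 54.2) |
| 2 | 75.0% (58.8 to 87.3) | 35.0% (20.6 to 51.7) |
| 4 | 70.0% (53.5 to 83.4) | 30.0% (16.6 to 46.5) |

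**The case against.** **The form is not shown.** As named in the SAP, the remap items are not expressly limited to the day of the remap. A reader might infer that an interval re-ablation can never be labelled reablated. The documents do not support that: the last row of the first table gives reablated, and so would a vein that reconnects again and is treated at remap. This limits how certain the miscoding is, but it does not rescue the rule, because the other history-based answers leave the subject in no category.

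**The definitions already point the right way.** CPS requires persistent isolation, and extra-PV durability means unaltered integrity. A site applying those words could mark a re-treated lesion as not durable. That is fair, but it leaves the result to each site's reading, and SAP 2.5 neither states the rule nor checks it.

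**Total CPS does not move.** On the status reading this stands: index-only and reablated both count as success, and the Table 13 shell has a single CPS row. The protocol and SAP 2.4.6.2 still require the split, and the durability rows move regardless.

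**The frequency is unknown.** A reader might take the rehospitalisations for atrial arrhythmia in the earlier studies (3/40 = 7.5% and 3/60 = 5%) as a repeat rate and infer a bias of 5 to 7.5 points. The documents do not say that any of those patients was ablated again, or that the event preceded the remap. No rate can be drawn from them, and it may be zero.

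**The listings may show these cases.** Listing 12 covers additional ablation, but its content is not given, and a listing does not change a derived endpoint.

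**Conclusion.** The gap is real. The protocol foresees a repeat ablation before the remap, and no SAP 2.5 durability rule accounts for it. If the remap items record status at remap, re-treated veins and lesions that are then intact are credited to the index procedure. If they are answered by history, most such subjects are unclassified.

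The index-only/reablated split and the vein, CTI and extra-PV durability rows are affected. Total CPS is unchanged on the status reading. The size is 2.5 points of index-only CPS per affected subject at n = 40 (4 at n = 25). The vein row moves by about 0.6 points per re-treated vein (1.0 at n = 25), assuming four veins per subject. How many subjects are affected cannot be known from the documents. With none, the effect is nil.

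**What to change.** In SAP 2.5:

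1. Add an indicator for any ablation between index and remap, with either a study or a non-study device, taken from the visit data and recording the structures treated.
2. Assign index-only CPS only to subjects with no pulmonary vein ablation in that interval. Code those with an interval pulmonary vein re-ablation and all veins isolated at remap as reablated CPS. A repeat confined to the CTI or other extra-PV sites leaves the pulmonary vein category unchanged. Disqualifying a subject for any interval ablation would be too broad, since CPS concerns the veins alone.
3. In the vein, CTI and extra-PV index-durability rows, use the documented status before ablation at the interval procedure where there is one. Otherwise count a re-treated vein or lesion as not durable.
4. Add a sensitivity row that excludes re-treated veins and lesions of unknown prior status, and state their number. Exclusion should not be the main rule: these are likely failures, and dropping them would still favour durability.

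The cost is a few lines of SAP logic and possibly a slightly lower durability figure. Whether the visit data identify the structure treated is not shown. The index steps call for a documented vein assessment but do not name a matching one for the CTI or other lesions, so the default in step 3 may apply more often to those.
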